3.2. Number of Patients

A total of 33 patients are planned: 21 in Part 1 (age 12 years to < 18 years), and 12 in Part 2. Part 2 of the study will only commence upon written approval of an amendment to this protocol by applicable regulatory bodies (i.e., IEC/IRB, MOH, and CA, as appropriate).

3.3. Treatment Assignment

Each patient will receive an open-label, single oral dose of betrixaban as specified in Section 3.1. The first 3 patients in the study will be assigned to Cohort 1 in the study. Subsequently, Sponsor/study management will centrally maintain and provide Sequence assignments.

3.4. Enrollment

A patient is considered to be enrolled in the study at the time the patient's parent or guardian signs the Informed Consent Form. Subjects will be replaced if they do not receive study medication.

3.5. Dose Adjustment Criteria

Not applicable.

3.6. Duration of Study

The duration of the study for each individual patient may be up to approximately 37 days (screening period of up to 30 days, Day -1, followed by administration of a single dose of betrixaban on Day 1, followed by blood sampling on Days 1, 2, and 6, and a safety follow-up phone call on Day 7).

The study is expected to enroll over approximately 50 months.

3.7. Data Safety Monitoring Board

There is no Data Safety Monitoring Board (DSMB) for this single-dose PK study.

3.8. Criteria for Study Termination

3.8.1. Halting or Termination of Enrollment

In the event of a Serious and Unexpected Adverse Reaction (SUSAR) or an episode of major bleeding, patient enrollment will be halted until a full accounting of the event and determination of its relationship to betrixaban has been completed by the Sponsor.

Major bleeding is defined as follows:

- Fatal or a life-threatening bleeding.
- Clinically overt bleeding resulting in a rapid decrease in hemoglobin level of more than 2 g/dL in 24 hours.
- Bleeding that is retroperitoneal, pulmonary, intracranial, or otherwise involves the central nervous system.
- Bleeding that requires a transfusion of a blood product and which is not directly attributable to the patient's underlying medical condition.
- Bleeding that requires surgical intervention in an operating suite.

If a patient is noted to develop a new QTc interval longer than 450 msec, or if change from baseline QTc interval of > 10 msec is observed in any patient, enrollment will be halted.

3.8.2. Sponsor Termination of the Study

The Sponsor may terminate the study at any time, for any reason. Typical reasons for termination of a study include, but are not limited to, the following:

- Unacceptable rate of enrollment.
- Unacceptable difficulty encountered with administration of study medication (e.g., patient cannot swallow or vomits medicine).
- Unacceptable incidence of AEs, including SUSARs or prolonged QTc interval, as noted in Section 3.8.1.
- Unacceptable incidence of noncompliance (e.g., notable percentages of patients refuse to allow blood sampling or provide urine samples).

3.8.3. Individual Patient Withdrawal

Criteria for withdrawal of individual patients as well as reporting procedures for AEs associated with halting or termination of enrollment are provided in Section 9.2.

The Schedule of Assessments for Study 16-021 is provided in Table 5.

	Screening	Day-1 ^a	Pre-Dose			Post Do	se 0.5 to 24 l	Hours (Day 1	- Day 2)			Post Dose 120 Hours	Day 7 Follow-up Phone Call
Procedure/Assessment	(≤ 30 days prior to dosing)	(Day -4 to Day -1)	(Day 1)									(Day 6)	
Time:	NA	NA	0.0 hr	0.5 hr	1.0 hr	2.0 hr	3.0 hr	4.0 hr	6.0 hr	12 hr	24 hr	120 hr	
Window:	NA	NA	NA	5 min	± 5 min	± 5 min	± 10 min	± 10 min	± 10 min	± 20 min	± 30 min	± 120 min	
Study Day:	-30 > -1	-4 > -1	1	1	1	1	1	1	1	1	2	6	7
General													
IC/Assent	Х												
Eligibility	Х	Х	Х										
Medical History	Х	Х											
Full PE ^b /Limited PE ^c	X ^b	X ^c									X ^c	X ^c	
Height (cm)	Х												
Weight (kg)	Х	Х									Х	Х	
Vital Signs / Temp	Х	Х	Х	Х	Х	Х	Х	Х	Х	Х	Х	Х	
Safety													
AE's (continuous)	Х	Х	Х			[X]			Х
Con Meds (continuous)	Х	Х	Х			[X]			Х
12-lead ECG	Х						Х				Х		
Local Safety Labs (Hem., Coag., Chem.)	Х	Х									Х	Х	
Urinalysis (to include blood in urine)	Х	Х									Х	Х	
Serum pregnancy (for females of childbearing potential)	Х	Х											
Stool for occult blood	[}	<]				[X, if/wh	en sample av	vailable]					
Urine drug screen (age 12 to <18 only)	Х	Х											
Fluid restriction			at least 1 hr pre-dose	at least 1 h	r post-dose								
Food restriction				at leas	st 2 hrs post	-dose							

Table 5:Schedule of Assessments: Study 16-021 (2 Pages)

Betrixaban

	Screening	Day-1 ^ª	Pre-Dose	Post Dose 0.5 to 24 Hours (Day 1-Day 2)						Post Dose 120 Hours	Day 7 Follow-up Phone Call		
Procedure/Assessment	(≤ 30 days prior to dosing)	(Day -4 to Day -1)	(Day 1)									(Day 6)	
Time:	NA	NA	0.0 hr	0.5 hr	1.0 hr	2.0 hr	3.0 hr	4.0 hr	6.0 hr	12 hr	24 hr	120 hr	
Window:	NA	NA	NA	5 min	± 5 min	± 5 min	± 10 min	± 10 min	± 10 min	± 20 min	± 30 min	± 120 min	
Study Day:	-30 > -1	-4 > -1	1	1	1	1	1	1	1	1	2	6	7
Cohort 1 - Rich Sampling													
Dosing under fed conditions			Х										
PK Sampling - BTX			Х	Х	Х	Х	Х	Х	Х	Х	Х	Х	
PD sampling - anti-fXa; TGI			Х			Х	Х				Х	Х	
Cohort 2 - Sequence A Sampling													
Dosing under fed conditions			Х										
PK Sampling - BTX			Х		Х		Х			Х		Х	
PD sampling - anti-fXa; TGI			Х		Х		Х			Х		Х	
Cohort 2 - Sequence B Sampling													
Dosing under fed conditions			Х										
PK Sampling - BTX			Х	Х		Х		Х			Х		
PD sampling - anti-fXa; TGI			Х	Х		Х		Х			Х		
Cohort 3 - Sequence C Sampling													
Dosing under fed conditions			Х										
PK Sampling - BTX			Х			Х	Х			Х	Х		
PD sampling - anti-fXa; TGI			Х			Х	Х			Х	Х		

^a Unless performed \leq 3 days prior to Day -1, i.e., on Days -4, -3, -2, and -1.

^b Complete PE as described in Section 9.1.2.1.

^c Brief PE as described in Section 9.1.2.2.

4.0 SELECTION AND WITHDRAWAL OF PATIENTS

To be eligible for enrollment in the study, a patient must meet *all* of the inclusion and *none* of the exclusion criteria as shown below. All entry criteria must be satisfied within 30 days of enrollment.

4.1. Inclusion Criteria

- Pediatric patients in the following age categories: 12 to < 18 years of age, and 2 to
 < 12 years of age. Part 1 of the study will enroll only adolescent patients 12 to
 < 18 years of age.
- 2. Patient is a pediatric subject who is assessed to be at risk for VTE but does not require immediate anticoagulant therapy, for example:
 - a. Has previous thrombosis and completed a course of anticoagulant therapy, and is considered to have a risk for recurrence of VTE; or
 - b. Has any stable disease with a risk for arterial or venous thromboembolism e.g. inflammatory or autoimmune disease, estrogen use within past 2 months, obesity, congenital heart disease, oncologic diagnosis, hip or knee reconstruction, family history of thromboembolism, immobility, trauma, surgery or lower extremity bone fracture, or
 - c. Has any functional Central Venous Access Device (CVAD) in the upper or lower venous system.
- 3. Patient must be able to have regular intake of a small amount of food (e.g., ≥ 100 mL) and eat before taking study medication, when instructed.
- 4. Patient has normalized coagulation parameters (INR or PTT, as appropriate) within 7 days of study drug administration.
- 5. Patient is sexually abstinent or, if not sexually abstinent, agrees to use an approved method of contraception (if applicable).
- 6. Patient has adequate venous access to allow for blood sampling.
- 7. Patient has provided Assent and the Informed Consent Form has been signed by the responsible parent(s) or guardian(s) in accordance with applicable local laws and regulations.

4.2. Exclusion Criteria

Patients who meet *any one* of the following exclusion criteria will be excluded from the study:

- 1. Patient received any dose of anti-coagulant therapy within 7 days of Day 1.
- 2. Patient has active bleeding or has a comorbid disorder that places the patient at high risk for bleeding, including a positive fecal occult blood test or hematuria within 30 days prior to Day -1.

- 3. Patient has a comorbid disorder that places the patient at risk of death within 90 days of enrollment.
- 4. Patient has abnormal coagulation tests at baseline (within 3 days of Day -1).
- 5. Patient has had recent or planned invasive procedures, including lumbar puncture and removal of non-peripherally placed central lines during study.
- 6. Patient has hepatic disease associated with one or more of the following:
 - Transaminase levels $\ge 2.5 \times \text{ULN}$ or bilirubin $\ge 1.5 \times \text{ULN}$ at baseline.
 - \circ Coagulopathy leading to a clinically relevant bleeding risk, or hepatic transaminase level of > 2 × ULN or total bilirubin > 2 × ULN with direct bilirubin > 20% of the total.
 - Platelet count $< 75 \times 109/L$ or hemoglobin < 10.0 mg/dL.
 - Hypertension.
- 7. Patient has known congenital or acquired bleeding diathesis.
- 8. Patient requires concomitant therapy with a strong P-gp inhibitor.
- 9. Patient has previous history of any non-traumatic bleeding event that was life threatening or required medical attention.
- 10. Patient had been administered thrombolytic therapy, or had undergone thrombectomy, or insertion of a caval filter to treat prior VTE.
- 11. Patient has known inherited or acquired bleeding diathesis or coagulopathy.
- 12. Patient has abnormal QTc interval on baseline ECG.
- 13. Patient will/has receive(d) a dose of any antiplatelet medication (including aspirin) within 14 days before study drug dosing. Planned or anticipated use of antiplatelet medication (including aspirin) in the first 24 hours following dosing shall exclude the patient.
- 14. Patient has malabsorption disorders (e.g., cystic fibrosis or short bowel syndrome).
- 15. Patient has an estimated Glomerular Filtration Rate (eGFR) < 30 mL/min.
- 16. Patient is unable or reluctant to cooperate with the study procedures.
- 17. Patient has hypersensitivity to other Factor Xa inhibitors, or the components of the dosage form.
- 18. Patient has participated in a study with an investigational drug or medical device within 30 days prior to administration of betrixaban.
- 19. Patient is female and of childbearing potential and is either pregnant or breastfeeding a child.

- 20. Patient is sexually active and is not using medically accepted contraceptive method (if applicable).
- 21. Patient has positive drugs of abuse urine test (age 12 to <18 years only) at Screening excluding medications prescribed by a physician during the current hospital stay.

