## **1.0 INTRODUCTION**

This document details the statistical analyses that will be performed to evaluate the pharmacokinetics and safety of betrixaban in pediatric patients enrolled in Study 16-021. Documents related to this analysis plan are:

• Betrixaban Study Protocol, titled "A Phase 1, Open-Label, Single-Dose, Non-Randomized Study to Evaluate Pharmacokinetics, Pharmacodynamics, and Safety of Betrixaban in Pediatric Patients"

Betrixaban, an oral direct FXa inhibitor, is approved in the United States for the indication of:

• prophylaxis of venous thromboembolism (VTE) in adult patients hospitalized for an acute medical illness who are at risk for thromboembolic complications due to moderate or severe restricted mobility and other risk factors for VTE.

The present study, Study 16-021, was performed to evaluate the pharmacokinetics, pharmacodynamics, and safety of betrixaban in pediatric patients.

Study 16-021 was originally designed to have 2 parts, however, Portola has elected not to continue to the development of betrixaban, thus only part 1 of this study was performed.

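### Exclusion 6 prints its hemoglobin limit in mg/dL, so it can exclude nobody, and it lists platelets, hemoglobin and hypertension under hepatic disease without making clear whether they apply to other children

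*Protocol*

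**What the plan says.** Exclusion 6 in Protocol Section 4.2 begins "Patient has hepatic disease associated with one or more of the following". Its sub-items are a transaminase or bilirubin limit, a coagulopathy item with further liver-test limits, a single line holding a platelet limit (75 x 10^9/L) "or hemoglobin < 10.0 mg/dL", and hypertension, with no definition. The synopsis has the same lead-in, the same items and the same hemoglobin unit.

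Elsewhere the protocol gives hemoglobin in g/dL. One of the major-bleeding definitions in Section 3.8.1, which halt enrollment, is a "rapid decrease in hemoglobin level of more than 2 g/dL in 24 hours".

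Other exclusions deal with bleeding in words. Exclusion 2 covers active bleeding or a "comorbid disorder that places the patient at high risk for bleeding, including a positive fecal occult blood test or hematuria". Exclusion 4 reads "Patient has abnormal coagulation tests at baseline", with a time window. Exclusions 7 and 11 cover known bleeding diathesis. Exclusion 9 covers a "previous history of any non-traumatic bleeding event that was life threatening or required medical attention".

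On numbers, Section 3.2 states that "33 patients are planned: 21 in Part 1 (age 12 years to < 18 years), and 12 in Part 2". SAP Section 1.0 says that development was stopped, "thus only part 1 of this study was performed".

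**The concern.** This is an entry safety criterion for a factor Xa inhibitor given to children. Inclusion 2 admits children with a stable oncologic diagnosis (2b) and any child with a working central venous access device (2c), so a low platelet count or low hemoglobin at screening is plausible.

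Two things look wrong. The hemoglobin limit as printed cannot be met. Separately, the lead-in makes liver disease a condition for every item below it, so correcting the unit alone would still leave no numeric hemoglobin limit for a child without liver disease. The same holds for platelets and hypertension.

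What is at stake is consistent eligibility across sites. One site might apply the platelet and hemoglobin limits to every child and another only to children with liver disease, and both could say they followed the text. Section 11.5 tells investigators not to deviate and routes changes through an amendment, so the literal wording matters.

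**Working it through.** **Inputs.** Printed limit: 10.0 mg/dL (Section 4.2 and synopsis, exclusion 6). Fall that counts as major bleeding: 2 g/dL (Section 3.8.1). Planned patients: 33, of whom 12 are in Part 2 (Section 3.2). Cohort sizes: 3 and 18 (Section 3.1).

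**Unit.**
- Limit in g/dL = limit in mg/dL / 1,000 = 10.0 / 1,000 = 0.010 g/dL.
- Intended over printed, if g/dL was meant: 10.0 / 0.010 = 1,000.
- Fall in Section 3.8.1 over printed limit: 2 / 0.010 = 200. A child whose hemoglobin can fall by 2 g/dL must start at 200 times the printed limit or more, so the protocol's own halting rule shows that the limit is not a workable value.

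**Structure.** Exclusion 6 has the form: hepatic disease AND (liver tests OR coagulopathy item OR platelets OR hemoglobin OR hypertension). If the first term is false, the whole criterion is false.

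| Item | As printed | Unit corrected only | Unit corrected and listed separately |
|---|---|---|---|
| Hemoglobin | Excludes nobody | Children with hepatic disease only | All children |
| Platelets | Children with hepatic disease only | Same | All children |
| Hypertension | Children with hepatic disease only | Same | All children |

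**Does another criterion fill the gap?**
- Exclusions 2, 7, 9 and 11 give no hemoglobin, platelet or blood-pressure value.
- Exclusion 4 concerns coagulation tests. Section 9.1.6.1 defines that panel as aPTT and PT/INR and puts the platelet count in the CBC, so exclusion 4 does not reach platelets.
- The pre-dose laboratory review in Section 7.3.1.1 checks eligibility against the written criteria. It does not add a limit.
- The protocol does write a general numeric limit as its own item where it wants one: exclusion 15 sets eGFR below 30 mL/min.

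**Evidence of intent.** The Amendment 2 entry on criterion 6 speaks of how pediatric hypertension is defined, leaves it to the investigator under regional and ethnic standards, and removes US blood pressure tables. That fits a general blood-pressure criterion better than a qualifier of liver disease. A change log cannot settle what the current text means, and it says nothing about the scope of the platelet or hemoglobin items.

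**Patients governed.** 33 - 12 = 21 = 3 + 18.

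**The case against.** The strongest reply is that the unit error is a misprint that no site would apply. The factors of 1,000 and 200 then measure a typing slip, not risk to a child. That stands: those figures show that the text is wrong and nothing more.

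The second reply is that the nesting may be deliberate. Platelets sit beside transaminases, bilirubin and coagulopathy and can be read as markers of serious liver disease. This also stands for platelets and hemoglobin. A reader might infer that general limits were meant and lost by mistake. The documents do not support that inference, because nothing states the scope intended for those two items. The reading fits hypertension less well.

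The third reply is that bleeding risk is already addressed for every child by exclusions 2, 4, 5, 7, 9, 11 and 13, by the requirement for normalized coagulation (inclusion 4) and by best-interest withdrawal (Section 4.3). Each patient takes one supervised dose (Section 5.3) and stays domiciled for 24 hours (Section 3.1). A reader might infer from the nesting that children without liver disease enter unprotected. They do not: an investigator could exclude severe thrombocytopenia or anemia on judgement. What is missing is a number, and with it uniformity between sites.

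Finally, leaving the definition of hypertension to the investigator looks like a recorded choice. I accept that. The gap is that the current criterion does not say so.

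**Conclusion.** The point holds in two parts of different strength.

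The unit is wrong in both places. The printed limit is 0.010 g/dL and the item excludes nobody. That g/dL was meant is an inference from Section 3.8.1 and from the impossibility of the printed value, but a safe one.

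The nesting is real in both places. Read literally, the platelet, hemoglobin and hypertension items do not apply to a child without liver disease, and no other criterion supplies a number. Whether that is an error is open for platelets and hemoglobin. For hypertension the amendment log points to a general criterion without proving it.

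The criterion governs the 21 planned Part 1 patients, since Part 2 was not performed. The documents give no count of children with low platelets, low hemoglobin or hypertension without liver disease, and do not show how sites read the criterion. A reader should not infer that any child was wrongly dosed. No PK parameter or analysis changes. The point is worth fixing because it concerns a pediatric safety criterion and the remedy is cheap.

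**What to change.** 1. Change mg/dL to g/dL in exclusion 6, in both Section 4.2 and the synopsis. This needs no further inquiry.
2. Ask the sponsor to confirm whether the platelet, hemoglobin and hypertension items were meant for all children. If so, list platelet count below 75 x 10^9/L, hemoglobin below 10.0 g/dL and hypertension (judged by the investigator against regional standards) as separate exclusions. If not, state that they apply only in hepatic disease, so that sites read the criterion alike.

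Cost: wording in two places and one question to the sponsor. No new tests are needed, because the CBC is already drawn at screening and Day -1 (Sections 7.1, 7.2 and 9.1.6.1) and blood pressure is part of vital signs (Section 9.1.3). The downside of stand-alone limits is somewhat narrower eligibility than the literal text, by an amount the documents do not let us estimate, in a study expected to enroll over about 50 months (Section 3.6). They could fall on groups that inclusion 2b names: the count limits on oncology patients, and the hypertension item on children with obesity or congenital heart disease. That is why confirmation should come before the change for all three items.

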4.3. Patient Withdrawal Criteria

Only one dose of study medication will be administered. Therefore, it is hoped that after patients take that dose, they will comply readily with the follow-up procedures (e.g., blood draws, urine sampling) specified for this Phase 1 study.

A patient who refuses to continue with study procedures is considered a "non-adherer." A patient who withdraws consent for any further contact with the study personnel is considered a "true withdrawer."

A patient can be withdrawn from the study for any of the following reasons:

- In the opinion of the Investigator, the patient cannot safely perform the procedures required by the protocol (e.g., provide blood or urine samples).
- The patient has an AE that is unacceptable to the patient or Investigator.
- The patient needs a concomitant medication that makes the patient ineligible for further participation in the study.
- The Investigator or Portola Pharmaceuticals, Inc. Medical Monitor decides it is in the patient's best interest not to continue in the study.
- The patient refuses to or cannot comply with study procedures, e.g., refuses study medication, blood sampling, or urine sampling ("non-adherer").
- The patient withdraws consent for any further contact with study personnel ("true withdrawer").

NOTE: Patients are free to withdraw from the study at any time for any reason. Reasons for all withdrawals will be recorded. If a patient discontinues the study due to an AE, that AE must be evaluated to determine whether it should be classified as a Serious AE (SAE). Any SAE that causes a patient to terminate the study must be reported by telephone to the Portola Pharmaceuticals, Inc. Medical Monitor immediately by the Investigator. The SAE form must be filed within 24 hours of awareness of the event. If feasible, all procedures described under the Study Termination Visit (Section 7.5) will be performed.

5.0 TREATMENT OF PATIENTS

5.1. Description of Study Drug

In Part 1, the investigational product, betrixaban capsules, is a hard gelatin capsule. A description of the study drug used in Part 1 is shown in . See Section 6.0 for details of packaging, labelling, administration, accountability, handling, and disposal.

Description of study drug for Part 2 of the study will be provided in an amendment to the protocol.

Name	Betrixaban capsules at 40 mg or 80 mg in pediatric patients 12 to < 18 years of age						
Dose	Single oral dose 40 mg or 80 mg						
Formulation	30% (as free base) betrixaban maleate						
	64.75% (w/w) dextrose monohydrate						
	1.25% (w/w) magnesium stearate						
	4% (w/w) croscarmellose sodium						
Physical Description	Size 2 gelatin capsule shell, or						
	Size 4 gelatin capsule shell						

Table 6:Description of Study Drug in Part 1

5.2. Concomitant Medications

5.2.1. Prohibited Medications

Ensure that the therapeutic course of anticoagulant has been fully discontinued and that the appropriate coagulation parameters (i.e., INR or PTT) have been confirmed as normal before the patient receives treatment with betrixaban.

The following medications are prohibited:

- Strong P-glycoprotein inhibitor
- Anti-platelets (including anti-inflammatory medications that exert anti-platelet effects)

5.2.2. Permitted Medications

The following medication is permitted:

• Acetaminophen for treatment of pain, if necessary

5.3. Treatment Compliance

Compliance will be assured by having the patient take the single dose of betrixaban while domiciled and under the supervision of study staff.

5.4. Randomization and Blinding

Not applicable. This is an open-label study.

6.0 STUDY DRUG MATERIALS AND MANAGEMENT

6.1. Study Drug

A description of the study drug, betrixaban capsules, is provided in Table 6.

